4.2 Interim Analysis Plan

[figure not shown]
Four analyses including three interim analyses and a final analysis are planned for the primary objective. The 3 interim analyses will follow a symmetric group sequential design using the alpha-spending methodology of Lan and DeMets² with O'Brien-Fleming³ type boundaries. Specifically, the cumulative alpha-spending function at the k^{th} look or analysis:

$$\alpha(t_k) = 2 - 2\Phi\left(\frac{Z_{\alpha/2}}{\sqrt{t_k}}\right)$$

where $k=1, 2, \dots, K$ and t_k is the information fraction at the k^{th} look, In the group sequential design for time-to-event endpoint, the information fraction at the k^{th} look can be defined as the cumulative count of events at the k^{th} look divided by the projected number of events at the final look.

The O'Brien-Fleming function was chosen because it conservatively preserves most of the type I error for the final analysis, and the conservation of type I error is desired due to the multiple endpoints and objectives of interest in this trial. The statistical stopping rules are illustrated in the figure below.

Figure 1: Statistical stopping boundaries

The horizontal axis shows the number of events, indicating the timing of interim analyses after 275, 550, and 825 events, and the final analysis when 1100 events are accrued. If at any interim analysis the standardized Z statistic for the primary objective is in the darker blue area with solid boundary line, the DMC may advise to stop the study claiming the null hypothesis is rejected. This corresponds to a cumulative α -level of 0.00002, 0.00304, 0.0193 and 0.05 spent at the subsequent stages (see section 5.1 “Error Spending Information” table). If the Z Statistic is in the lighter blue area with dashed boundary line, the DMC may advise to stop the study for futility.

In case the study is stopped for efficacy after an interim analysis, the secondary objectives will be analyzed using a family-wise type I error rate derived from a Pocock-type alpha-spending function. This corresponds to a cumulative α -level of 0.018, 0.031, 0.041 and 0.05 spent at the subsequent stages⁴. Hommel procedure will be used to correct for multiplicity.⁵ This will be implemented by the SAS MULTTEST procedure.

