the event or the date of last documented follow-up since randomization for those who are censored. Date of last documented follow-up since randomization is the maximum value among the dates of randomization, randomization programming, any study scheduled follow-up visit, exit, adverse event onset, adverse event resolved, system modification, and healthcare utilization. Rand is an indicator variable for randomized treatment groups (1=aCRT ON, 0=aCRT OFF).

The hazard ratio for treatment arm (aCRT ON) versus control arm (aCRT OFF) will be reported with its associated p-value and 95% confidence interval. The null hypothesis will be rejected when the p-value is below the critical value for the (interim or final) analysis. The actual cumulative α level will be calculated based on the actual number of primary events included in each interim analysis. The estimated cumulative α -level is approximately 0.00002, 0.00304, 0.0193 and 0.05 at the 1st interim with 275 events, 2nd interim with 550 events, 3rd interim with 825 events and the final analysis with 1100 events, respectively (see details in section 0). It will be concluded that aCRT reduces the incidence of the primary endpoint when the null-hypothesis is rejected and the hazard ratio is below 1. Kaplan-Meier plots for incidence of primary endpoint will be presented by treatment arms, for all patients and for the separate NYHA class groups. The absolute event rate difference at 2 years post randomization will also be calculated.

The following model assumptions will be checked:

1. Proportional hazards between treatment arms: an interaction term of treatment arm by time (in log scale) will be added into the model (see the code below). If this interaction effect is not significant, the proportional hazard assumption holds. Otherwise, this interaction term should be kept in the model as a remedy for non-proportional hazards, and any secondary analysis where treatment (or treatment by subgroup factor interaction) is included should also include the corresponding interaction term with time. Being time dependent, the treatment effect will be assessed every 6 months to the end of the follow-up to monitor the direction. Significance of the treatment effect will be based on its estimate at 24 months using a contrast.

```
PROC PHREG DATA=primary;  
  CLASS NYHA site;  
  MODEL time*event(0) = rand rand_t / TIES=efron;  
  rand_t = rand*log(time);  
  STRATA NYHA;  
  RANDOM site/ dist = gamma;  
RUN;
```

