4.3.4 Sensitivity Analyses: LBBB Determination and aCRT Programming

As indicated in section **Error! Reference source not found.**, two sensitivity analyses will be performed for the primary objective. One is an ITT analysis of the randomized patients whose LBBB is confirmed by the ECG Core Lab. The purpose of this sensitivity analysis is to verify the effect of aCRT on the incidence of HF events or death among the true LBBB patients and to assess the impact of LBBB misclassification on the results. This analysis will be conducted in a similar way to that of the primary analysis:

```
PROC PHREG DATA=LBBB;  
CLASS NYHA site;  
MODEL time*event(0) = rand / TIES=efron;  
STRATA NYHA;  
RANDOM site/ dist = gamma;  
RUN;
```

Here, 'event', 'time' and 'aCRT' are defined in the same way as those in the primary analysis. A p-value for treatment below the cumulative α -level of approximately 0.00002, 0.00304, 0.0193 and 0.05 at the 1st, 2nd, 3rd interim and the final analysis, respectively, is significant.

The other sensitivity analysis will also be conducted in the randomized patients with ECG Core Lab confirmed LBBB, while the purpose is to verify the effect of aCRT on the primary endpoint based on the actual aCRT programming over time. Given this being said, this analysis will not follow the ITT principle and:

- Patients with major eligibility violations will be excluded (also when the violation becomes apparent only after randomization).
- Patients with major protocol violations after randomization, such as being programmed permanently to a mode that deviated from original randomization assignment due to a system modification after randomization, will be censored at the time of protocol violations.
- Patients' actual aCRT programming will be a time-varying covariate that has 3 categories: ACRT ON, ACRT OFF, and Neither, counting from the time randomization programming is implemented.

This analysis will be conducted using the following SAS PHREG procedure:

```
PROC PHREG DATA=LBBBCross COVSANDWICH (AGGREGATE) ;  
  ID pt;  
  CLASS NYHA site pt;  
  MODEL (start,stop)*event(0) = aCRTprog / TIES=efron;  
  STRATA NYHA;  
RUN;
```

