where aCRTprog indicates patients' actual aCRT programming. Patients whose actual aCRT programming change over time get multiple records in the input dataset. Whenever there is a change, for instance, there will be one record in the randomized arm up until time of crossover and another record from time of crossover until the time that a primary endpoint is met or the time of censoring without meeting a primary endpoint. The COVSANDWICH option ensures the model accounts for multiple records coming from the same patient. In order to implement the COVSANDWICH option in SAS, random site effect will not be considered in this sensitivity analysis. A p-value for treatment below the cumulative α -level of approximately 0.00002, 0.00304, 0.0193 and 0.05 at the 1st, 2nd, 3rd interim and the final analysis, respectively, is significant.

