Based on the literatures^{8,9}, the following characteristics are expected in the final model: from enrollment form, gender, QRS duration, ECG Core Lab confirmed LBBB, LVEF, NYHA class, AV conduction time; from baseline form, age, BMI, SBP, rales/crackles, dyspnea, peripheral edema, HF admissions in past 6 months, creatinine, history of MI, AF, diabetes and smoking; from cardiovascular medication log, baseline diuretics dose, and ACE/ARB. If not, we might consider to add them into the final model in order to compare with the literature.

A risk score for the primary endpoint can be defined as $\mathbf{X}\beta$ with \mathbf{X} being the covariates remained in the final model.

The critical values for the treatment effect in the primary analysis (estimated cumulative α -level of approximately 0.00002, 0.00304, 0.0193 and 0.05 at the 1st, 2nd, 3rd interim and the final analysis, respectively) will not be applied to this ancillary analysis.

Multiple imputation will be used to handle missing values for the covariates in the multi-variable models. The SAS MI and MIANALYZE procedures will be used to conduct multiple imputation.

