4.4 Secondary Objectives

Secondary objectives include the two components of the primary endpoint, clinical composite score, incidence of atrial fibrillation, quality of life, all-cause re-admission after a heart failure admission, and cost effectiveness for the healthcare system.

Interpretation of results will be guided by a formal multiple testing procedure to achieve strict control of the family wise error rate, also accounting for the interim analysis plan. Secondary objectives will be analyzed when the study has stopped for efficacy after an interim analysis or has reached the final analysis stage. As indicated in section 0, the cumulative α -level to be spent at the 1st, 2nd, 3rd interim analysis and final analysis for secondary objectives is 0.018, 0.031, 0.041 and 0.05, respectively, corresponding to a Pocock-type alpha-spending function. At the analysis stage when secondary objectives are analyzed, a Hommel procedure^{5,13} will be applied to the secondary objectives (excluding the cost-effectiveness objective) to correct for multiplicity based on the cumulative α -level of that stage. Secondary objectives for which the hypothesis is rejected under the adjusted significance level of the Hommel procedure will be reported as significant.

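### The SAP uses cumulative alpha spent as p-value cut-offs, and leaves futility stopping discretionary although the design size fits binding futility; if futility never stops the trial, two-sided type I error is 0.055 to 0.056

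*SAP*

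**What the plan says.** **The rejection rule.** SAP 4.3.2 says that "The null hypothesis will be rejected when the p-value is below the critical value for the (interim or final) analysis". Protocol 11.3.2 has the same rule. No nominal value follows. The SAP gives approximate cumulative levels of 0.00002, 0.00304, 0.0193 and 0.05 at 275, 550, 825 and 1100 events, with the pointer "see details in section 0". No such section exists. SAP 4.4 uses the same pointer ("As indicated in section 0, the cumulative") for levels that are set out in 4.2, so 4.2 is probably meant. What is to be updated is again the cumulative quantity: the "level will be calculated based on the actual number of primary events included in each interim analysis".

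**The same levels used as cut-offs.** SAP 4.3.6 refers to "The critical values for the treatment effect in the primary analysis (estimated cumulative" and lists the four levels in that bracket. Both sensitivity analyses in SAP 4.3.4 use them as a test: "A p-value for treatment below the cumulative" level, with the values "0.00002, 0.00304, 0.0193 and 0.05 at the 1st, 2nd, 3rd interim and the final analysis, respectively, is significant".

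**The same levels as alpha spent.** SAP 4.2 and protocol 11.4 describe them as alpha spent by stage, and the interim decision rests on Z: "If at any interim analysis the standardized Z statistic for the primary objective is in the darker blue area with solid boundary line". The boundary values may be printed in that figure or in the SAP 5.1 output. Neither can be read in the public copy.

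**Futility.** SAP 4.2 says that the DMC may advise stopping for futility. Protocol Appendix C makes the DMC advisory and its boundaries guidelines only, and lets the DMC charter override the appendix. SAP 4.2 also gives priority to having enough cost-effectiveness information before any early stop. Against this, SAP 4.3.1 and protocol 5.1.1 have the study run to its event target unless the DMC advises stopping. The SEQDESIGN code in SAP 4.3.8 sets `stop = both`.

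**The concern.** Cumulative alpha spent and a stage-wise p-value cut-off are different quantities. After three earlier chances to reject, a test at p < 0.05 at the final look does not hold the overall level at 0.05 unless something else removes null trials along the way. A binding futility rule does that: it relaxes the final efficacy boundary by counting on trials that stop for futility. If the trial may continue after crossing the futility line, that credit is not earned.

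SAP 4.1 and protocol 11.1 promise an overall two-sided 0.05. The result most exposed is a final p between 0.044 and 0.050. It would be a success on the printed 0.05, but not on a cut-off that is valid whatever happens about futility.

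**Working it through.** **Inputs (SAP 4.3.8 unless noted).** Two-sided alpha 0.05, beta 0.10, HR 0.81818 (0.82 in the text), four equally spaced looks (t = 0.25, 0.50, 0.75, 1), O'Brien-Fleming-type error spending, `stop = both`, control hazard 0.14384, accrual 3 years, follow-up 2.25 years, 1:1 allocation (SAP 3).

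**1. The printed levels.** The SAP 4.2 formula is 2 − 2Φ(z(α/2)/√t).
- At α = 0.05 it gives 0.00009, 0.0056, 0.0236, 0.05, which are not the printed levels.
- At α = 0.025 per side, doubled, it gives 0.000015, 0.00305, 0.0193, 0.05, which match to rounding.

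**2. The 1100 events.** Events = 4θ²/ln(HR)², where θ is the drift giving 90% power and ln(0.81818)² = 0.04027. The futility bounds are assumed to come from O'Brien-Fleming-type beta spending.
- Binding futility: θ = 3.331, so 4 × 11.10 / 0.04027 ≈ 1102. Other treatments of overlapping early bounds give 1099 to 1101, and one-sided beta accounting gives 1092 to 1094.
- Non-binding futility: θ = 3.378, so about 1133. The variants give 1118 to 1132.
- No futility rule: 1063.

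**3. The 2874 patients.** The event probability per arm is 1 − [exp(−hF) − exp(−h(A+F))]/(hA), with A = 3 and F = 2.25. Averaged over arms it is 0.3829, and 2874 × 0.3829 ≈ 1100.5 events. Non-binding futility would need about 2920 to 2956 patients. Binding futility fits best.

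**4. Cut-offs compared.**

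| Look (events) | Printed level read as p, with its Z | Reconstructed binding Z | Non-binding Z (nominal p) |
|---|---|---|---|
| 275 | 0.00002 (4.265) | 4.333 | 4.333 (0.000015) |
| 550 | 0.00304 (2.964) | 2.963 | 2.963 (0.0030) |
| 825 | 0.0193 (2.340) | 2.358 | 2.359 (0.0183) |
| 1100 | 0.05 (1.960) | 1.962 | 2.014 (0.0440) |

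The assumed futility bounds on |Z| are 0.005, 0.351 and 1.237 at the three interim looks.

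**5. Two-sided type I error**, by numerical integration of Z√t, which has independent normal increments of variance 0.25 under the null:

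| Futility crossings acted on | Printed levels as cut-offs | Binding Z | Non-binding cut-offs |
|---|---|---|---|
| Never | 0.0558 | 0.0551 | 0.0500 |
| Each with probability one half | 0.0530 | 0.0524 | 0.0478 |
| Always | 0.0506 | 0.0500 | 0.0460 |

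With the printed levels and no futility stop, the looks contribute 0.00002 + 0.00303 + 0.01719 + 0.03554 = 0.0558. Simulation of 20 million null trials gives 0.0558 (printed levels) and 0.0552 (binding Z), never acted on. A final p between 0.044 and 0.050 without an earlier rejection has null probability 0.0054 in the never case.

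**6. Source of the excess.** Against the binding boundary, the label adds about 0.0006 in the never case and futility discretion the rest. Against the non-binding cut-offs, using the printed levels accounts for the whole excess, 0.0558 − 0.0500 = 0.0058. The split depends on the baseline.

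**7. Power at 1100 events.**

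| HR | Futility | Printed levels | Non-binding cut-offs |
|---|---|---|---|
| 0.82 | Never acted on | 91.2% | 90.3% |
| 0.82 | Always acted on | 89.4% | 88.7% |
| 0.81818 | Never acted on | 91.8% | 91.0% |
| 0.81818 | Always acted on | 90.0% | 89.4% |

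**The case against.** The strongest reply is that the operating rule is the Z boundary in SAP 4.2. SAP 4.3.2 names a critical value and then, separately, a cumulative level; it does not say they are the same. SAP 4.3.6 mentions the levels only to say they do not apply to the ancillary analysis, and 4.3.4 concerns sensitivity analyses. All of this is fair for the primary test, and a reader should not infer that the SAP contains no boundary, since the figure and the 5.1 output cannot be read. What stands is the conflict: two sections treat as p-value cut-offs what two other places call alpha spent.

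On futility, a reader might infer that the sponsor is free to set the DMC's advice aside. SAP 4.3.1 and protocol 5.1.1 point the other way, since advice to stop ends the study. The discretion lies mainly in whether a crossing leads to advice. The DMC charter, which takes priority over the appendix, may settle this and is not among the documents. No readable text calls futility binding, and the non-binding event counts lie within 3% of 1100.

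It is also fair that the present plan keeps 90% power at the coded HR of 0.81818 whether futility is acted on or not, and that committing to act on futility would restore the level too. That second route, however, would contradict the advisory wording in SAP 4.2 and Appendix C.

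**Conclusion.** The label conflict is real and should be corrected. On its own it is small: about 0.0006 measured against the reconstructed binding boundary. The larger issue is that the promised 0.05 appears to depend on futility stops that the plan does not require.

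The exposure is a range. Two-sided type I error is 0.055 to 0.056 if crossings never stop the trial, about 0.053 if half are acted on (0.052 with the binding Z boundary), and 0.050 to 0.051 if all are. A false claim of benefit has half the two-sided probability, so about 0.028 at worst against 0.025. It would go too far to say that the trial runs at 0.056: that needs every futility crossing to be passed over and the printed levels to be applied as cut-offs.

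Confidence is high for the text conflict and the arithmetic. It is moderate for the binding design, which rests on back-calculating 1100 events and 2874 patients under an assumed beta-spending bound.

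**What to change.** - In SAP 4.3.2, 4.3.4 and 4.3.6, label the four levels as cumulative alpha spent. Print nominal stage-wise cut-offs that hold whether or not futility is acted on: about 0.000015, 0.0030, 0.0183 and 0.0440 at 275, 550, 825 and 1100 events.
- State that they are recomputed at the actual event counts, including the final look. SAP 4.2 ties the SEQTEST update to interim looks only.
- State in SAP 4.2 that futility is non-binding, set the SEQDESIGN and SEQTEST code to match, and align the DMC charter.
- Repair the pointer to section 0, and note that the spending formula is applied at 0.025 per side and doubled.
- In SAP 4.3.8 and protocol 11.3.4, give the 90% power with its condition: with these cut-offs, 90.3% (HR 0.82) or 91.0% (HR 0.81818) if futility is not acted on, and 88.7% or 89.4% if it always is.

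The cost is wording, one code setting and under one point of power. At 1100 events the observed hazard ratio needed for significance moves from exp(−2 × 1.960/√1100) = 0.889 to exp(−2 × 2.014/√1100) = 0.886. Guaranteeing 90% with futility always acted on would take about 1133 events (HR 0.81818) or 1159 (HR 0.82). Stating the condition is preferable to adding events.

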11.3.2 Hypothesis, analysis methods and performance requirements

The null hypothesis that will be tested is that the hazard ratio for aCRT versus control is equal to 1. It will be tested against the alternative hypothesis that the hazard ratio is unequal to 1.

Let $S_T(t)$ and $S_C(t)$ denote the proportion of patients in the treatment arm and control arm, respectively, that have not experienced a primary endpoint up to time t . Let $h_T(t)$ and $h_C(t)$ be the associated hazard functions. Under the proportional hazards model, $h_T(t) = HR h_C(t)$, where HR is the hazard ratio of treatment compared to control. The null and alternative hypotheses can be expressed as:

$$H_0 : HR = 1$$

$$H_A : HR \neq 1$$

The hypothesis will be tested using a Cox proportional hazards regression model with a random center effect (frailty), stratified by baseline NYHA class. The hazard ratio for treatment arm versus control arm will be reported with its associated p-value and 95% confidence interval. The null hypothesis will be rejected when the p-value is below the critical value for the (interim or final) analysis, and it will be concluded that aCRT reduces the incidence of the primary endpoint when the hazard ratio is below 1. Kaplan-Meier graphs for incidence will also be reported, together with an estimate for the absolute event rate difference at 2 years post randomization.

Two further analyses of the primary objective are planned. First, a Cox regression model will be reported with a random center effect and a risk score as fixed effect. The risk score will be derived from baseline data. Second, an analysis will be done including only the patients for whom the ECG Core Laboratory confirmed the presence of LBBB.

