11.3.4 Sample size rationale

A total of 1100 patients experiencing a primary endpoint will give 90% power to show a significant reduction of the incidence of the primary endpoint, accounting for 3 equally spaced interim analyses and assuming a true intent-to-treat hazard ratio of 0.82 for aCRT ON compared to aCRT OFF.

Version 1.0 of the CIP specified the total number of patients randomized as follows: With the inclusion of 2874 randomized patients enrolled over 3 years and followed for 2.3 more years, 1100 primary endpoint events are expected when the true control arm event-free rate is 75% at 2 years.

Version 2.0 of the CIP increases the total number of patients randomized to accommodate a lower event rate: With the inclusion of 3326 randomized patients enrolled over 4 years and followed for 3.5 more years, 1100 primary endpoint events are expected when the true control arm event-free rate is 85% at 2 years.

The study will randomize approximately 3500 patients in order to accommodate attrition due to early exit. The study will be event-driven and the DMC may advise to stop enrollment early when the primary endpoint rate is higher than expected.

Through simulation it was confirmed for version 1.0 of the CIP that the study will have 90% power under the following assumptions:

- 3000 patients randomized in 3 years with a uniform rate

[figure not shown]
- control arm event-free rate is 75% at 2 years
- LBBB is not confirmed by the ECG Core Laboratory in 10% of patients
- aCRT hazard ratio is 0.78 in confirmed LBBB patients, 1.0 in unconfirmed patients
- crossover rate is 5% at 2 years in aCRT arm and 8% at 2 years in control arm
- loss-to-follow-up rate is 5% at 2 years in both arms
- final analysis is done when 1100 events are accrued

For version 2.0 of the CIP, the simulation was updated and the power of 90% was confirmed with updated control group event rate expectation.

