4 DESCRIPTION OF ANALYSIS

4.1 General

Medtronic employed statisticians will perform the statistical analyses described in this SAP. Interim analyses will be performed by a Medtronic statistician other than the lead statistician for the study. The lead study statistician will be blinded to all interim analyses.

All tests of treatment effects will be conducted in order to preserve an overall two-sided alpha level of 0.05 unless otherwise stated. An Intention-to-Treat analysis will be performed and will serve as the primary analysis for all objectives in this study. The Intention-to-Treat cohort will include all randomized subjects.

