The required number of HF event or death to get 90% overall study power is estimated using the following SAS SEQDESIGN procedure (also Section 5.1):

```
proc seqdesign
  boundaryscale=stdz
  errspend
  stopprob
  plots=boundary(hscale=samplesize);
;
Interim: design
  alpha = 0.05
  alt = twosided
  beta = 0.10
  stop = both
  nstages = 4
  method = errfuncobf
;
samplesize
  model = twosamplesurv
  ( nullhazard = 0.14384
    hazardratio = 0.81818
    acctime = 3.0
    foltime = 2.25
  );
run;
```

that assumes:

- Type I error rate: 0.05
- Type II error rate: 0.10, which corresponds to 90% power
- 3 equally spaced interim analyses plus the final analysis
- Hazard of aCRT OFF arm: 0.14384
- Hazard ratio of aCRT: 0.81818
- Enrollment duration: 3 years
- Follow-up duration: 2.25 years

The results (Section 5.1) show that a total of 1100 patients experiencing a primary endpoint will give 90% power to detect a reduction of the incidence of the primary endpoint at a significance level of 0.05, accounting for 3 equally spaced interim analyses and assuming a true intent-to-treat hazard ratio of 0.82 for aCRT ON compared to aCRT OFF.

With the inclusion of 2874 randomized patients enrolled over 3 years and followed for 2.3 years, 1100 events are expected when the true event-free rate of aCRT OFF arm is 75% at 2 years.

The study will randomize up to 3000 patients in order to accommodate attrition due to early exit and to accommodate the possibility of a somewhat lower control arm event rate. Through simulation (Section 1.1) it was confirmed that the study will have 90% power under the following assumptions:

- 3000 patients randomized in 3 years with a uniform rate
- Event-free rate of aCRT OFF arm is 75% at 2 years
- LBBB is not confirmed by the ECG Core Lab in 10% of patients
- aCRT hazard ratio is 0.78 in confirmed LBBB patients and 1.0 in unconfirmed patients
- Crossover rate at 2 years is 5% in aCRT ON arm and 8% in aCRT OFF arm
- Loss to follow-up rate is 5% at 2 years in each arm
- Final analysis is done when 1100 primary events are accrued

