4.4.1 Secondary Objective #1: All-cause mortality

The secondary objective #1 is to test the hypothesis that aCRT ON reduces all-cause mortality compared to aCRT OFF. All-cause mortality is one of the two components that comprise the primary endpoint.

Hypothesis

Let $S_T(t)$ and $S_C(t)$ denote the proportion of patients in the treatment arm (aCRT ON) and control arm (aCRT OFF), respectively, that have not died up to time t . Let $h_T(t)$ and $h_C(t)$ be the associated hazard functions. Under the Cox regression model that assumes proportional hazards, $h_T(t) = HR \cdot h_C(t)$, where HR is the hazard ratio of treatment compared to control. The null and alternative hypotheses are:

$$H_0 : HR = 1$$

$$H_A : HR \neq 1$$

Analysis Method

Similar to the primary endpoint, the hypothesis regarding the aCRT effect on all-cause mortality will be tested using a Cox proportional hazards regression model with a random site effect (frailty), stratified by NYHA class at enrollment. Section 4.3.2 has described this model in details. The analysis will be conducted using code similar to:

```
PROC PHREG DATA=mortality;  
  CLASS NYHA site;  
  MODEL time*death(0) = rand / TIES=efron;  
  STRATA NYHA;  
  RANDOM site/dist = gamma;  
RUN;
```

In these codes, death = 1 given an adjudicated death and death = 0 otherwise; time to death starts from the date of randomization and ends at the date of death for those who die, or the date of last documented follow-up since randomization for those who are censored. Date of last documented follow-up since randomization is the maximum value among the dates of randomization, randomization programming, any study scheduled follow-up visit, exit, adverse event onset, adverse event resolved, system modification, and healthcare utilization.

The model assumptions will be checked using the same methods that are described in detail in section 4.3.2 for the primary endpoint. That is, the assumption of proportional hazards between the treatment arms will be checked by testing the significance of treatment by time interaction term; and, the assumption of constant hazard ratio for treatment across NYHA classes will be checked by testing the significance of treatment by NYHA class interaction and evaluating the hazard ratio for treatment within each NYHA class.

Missing Data

Similar to the analysis for primary endpoint, we assume non-informative censoring for lost to follow up in the analysis of all-cause mortality.

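### A proportional-hazards pre-test in SAP 4.3.2 can move the primary decision from the Cox treatment coefficient to a modelled 24-month hazard ratio, for which the boundaries were not built

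*SAP*

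**What the plan says.** Protocol 11.3.2 states H0: HR = 1 and one way of testing it: "The hypothesis will be tested using a Cox proportional hazards regression model with a random center effect (frailty), stratified by baseline NYHA class". It contains no step that replaces this test.

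SAP 4.3.2 sets up the same model and then lists two assumption checks. The first adds treatment by log(time). If the term is not significant, proportional hazards is taken to hold. If it is significant, the term is kept, the effect is reported every six months, and "Significance of the treatment effect will be based on its estimate at 24 months using a contrast". No significance level is given for the check, nor the looks at which it is made, nor a boundary for the contrast. The code shown contains no contrast statement. The second check tests treatment by NYHA class; if that is significant, the primary model changes and effects are reported by class.

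SAP 4.2 measures information by event counts: "The horizontal axis shows the number of events, indicating the timing of interim analyses after 275, 550, and 825 events". SAP 4.3.8 rests the design on one sequence of Z statistics with the canonical joint distribution. SAP 4.1 commits to an error rate: "All tests of treatment effects will be conducted in order to preserve an overall two-sided alpha level of 0.05 unless otherwise stated".

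On mortality, SAP 4.4.1 says: "The model assumptions will be checked using the same methods that are described in detail in section 4.3.2 for the primary endpoint". SAP 4.4.2 and 4.4.4 say the same for heart failure events and AF. All three then restate the checks, but not the 24-month rule.

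**The concern.** The sentence on the 24-month contrast is a decision rule, not a diagnostic. It makes the primary test a two-step procedure in which the observed time pattern selects the statistic. A sequence of Z values that may change from the Cox coefficient to a time-specific contrast is not the sequence for which the boundaries were derived.

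Two things are at stake. One is the overall two-sided 0.05. The other is the meaning of a positive or negative result: the stated hypothesis concerns one hazard ratio over follow-up, whereas after the switch the verdict rests on one instantaneous hazard ratio read from a log-linear curve.

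**Working it through.** **1. The plan's own figure.** Protocol 11.3.4: "A total of 1100 patients experiencing a primary endpoint will give 90% power", "assuming a true intent-to-treat hazard ratio of 0.82 for aCRT ON compared to aCRT OFF". The SAP 4.3.8 run uses "Hazard ratio of aCRT: 0.81818". With 1:1 allocation:

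D = 4(1.960 + 1.282)² / (ln 0.81818)² = 42.03 / 0.04027 = 1044.

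Four looks with O'Brien-Fleming-type spending and binding futility stops inflate this by 1.0585, giving 1105 against the stated 1100. Spending 0.025 on each side gives cumulative alpha 0.0000147, 0.00305, 0.0193 and 0.05, in line with the stated values. The design figure is therefore reproduced, for the plain test.

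**2. Precision of the contrast.** The plain log hazard ratio has variance 4/D. With the interaction in the model, the log hazard ratio at 24 months has variance

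(4/D) × [1 + (ln 24 − m)² / s²],

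where m and s² are the mean and variance of log event time. Inputs are protocol version 2.0 (3326 patients, 4-year accrual, 85% event-free at 2 years), exponential times and no loss. At the first look the geometric mean event time is 7.5 months (m = 2.015) and s² = 1.30, so the ratio to 4/D is 1 + (3.178 − 2.015)²/1.30 = 2.04.

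| Events | Variance ratio | Information fraction, plain | Information fraction, contrast | Events after month 24 |
|---|---|---|---|---|
| 275 | 2.05 | 25% | 0.25 × 1.03/2.05 = 13% | about 9% |
| 550 | 1.51 | 50% | 0.50 × 1.03/1.51 = 34% | about 25% |
| 825 | 1.18 | 75% | 0.75 × 1.03/1.18 = 65% | about 40% |
| 1100 | 1.03 | 100% | 100% | |

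Under version 1.0 inputs (2874 patients, 3-year accrual, 75% event-free at 2 years) the ratios are 2.78, 2.06, 1.62 and 1.29. The first look then comes about 2.1 years after first randomization, with essentially no events beyond month 24.

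**3. Type I error.** Whole trials were simulated with HR = 1 throughout, looks at 275, 550, 825 and 1100 events, efficacy bounds 4.33, 2.96, 2.36 and 2.01, no forced futility stop, and 5% loss at 2 years. Frailty and NYHA strata were left out. The check was applied at every look, at an assumed level.

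| Inputs | Trials | Plain Cox | Check at 0.01 | 0.05 | 0.10 |
|---|---|---|---|---|---|
| v2.0: 3500 patients, 4 years, 85% | 25,000 | 0.049 | 0.051 | 0.054 | 0.056 |
| v1.0: 3000 patients, 3 years, 75% | 12,000 | 0.049 | 0.054 | 0.061 | 0.065 |

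The Monte Carlo standard errors are √(0.05 × 0.95/25,000) = 0.0014 and √(0.05 × 0.95/12,000) = 0.0020, so the result was also checked by a large-sample normal calculation of the same rule. With the check at 0.05 this gives 0.052 to 0.054 (v2.0, depending on patient number and loss) and 0.061 (v1.0).

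Under v2.0, with the check at 0.05, the test switches at one or more looks in about 12% of null trials. Crossing rates rise from 0.0031 to 0.0043 at 550 events and from 0.0180 to 0.0206 at 825.

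With a single analysis at 1100 events, the simulated two-step error is 0.050 (plain 0.049) under v2.0 and 0.053 (plain 0.0475) under v1.0. The large-sample values are 0.051 and 0.056. The excess thus arises mainly at the interims under v2.0; under v1.0 about half of it remains in a single analysis.

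**4. Rejection when there is an effect (v2.0, check at 0.05).**

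| True hazard ratio | Plain Cox | Two-step |
|---|---|---|
| 0.82 throughout | 0.901 | 0.902 |
| 0.70 to month 24, then 1.10 | 0.45 | 0.36 |
| 0.65 to month 12, then 1.0 | 0.35 | 0.29 |
| 1.0 to month 12, then 0.75 | 0.942 | 0.957 |

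In the third row the modelled 24-month hazard ratio averages 0.93, although the true value there is 1.0.

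**The case against.** The strongest reply is that the rule is written down: the log form, the trigger and the 24-month point are all stated. Protocol 11.1 lets the SAP add detail and requires deviations to be explained. Twenty-four months also matches the 2-year event-rate difference in protocol 11.3.2. A reader might infer that the analyst is free to pick a test, and the documents do not support that. The unstated check level and timing do leave room for choice.

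A reader might also infer that error control fails badly. It does not: the excess under version 2.0 is a few thousandths, power at constant HR 0.82 is unchanged, and protocol Appendix C treats the boundaries as guidance for the DMC. Version 1.0 inputs give the larger excess, and protocol 11.3.4 has replaced them, although the SAP still carries them.

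A third inference is that the contrast is an extrapolation at every interim. Under version 2.0 that is mainly true of the first look, which spends only 0.00002.

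A fourth is that the 24-month rule governs mortality, heart failure events and AF. The SAP cites the same methods but restates only the checks, so the carry-over is an inference.

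Finally, under non-proportional hazards the Cox coefficient is itself an average that depends on follow-up, so the power differences partly reflect a choice of estimand. That is fair. But the protocol made that choice, and the 1100 events and the boundaries were built for it.

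**Conclusion.** The point stands in a limited form. Whenever the check is significant, the SAP takes the primary decision from a statistic that the protocol does not name and that has no boundary. The promised two-sided 0.05 is then not exactly kept: about 0.054 under version 2.0 inputs and 0.061 under version 1.0.

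The heavier consequence is that the hypothesis changes. Under non-proportional hazards the verdict can move in either direction according to where in follow-up the effect lies.

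These sizes assume a check at every look, a level between 0.01 and 0.10, exponential event times under the null, reconstructed boundaries, and no frailty or NYHA strata.

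**What to change.** Replace the sentence in SAP 4.3.2 with: *At every look the primary hypothesis is decided by the treatment coefficient of the NYHA-stratified Cox frailty model of CIP 11.3.2, whatever the result of the model-assumption checks; the rand × log(time) model, the 24-month contrast and the 6-monthly hazard ratios are supportive only.*

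State also that the NYHA-interaction check in the same section does not change the deciding test, and that the checks in 4.4.1, 4.4.2 and 4.4.4 do not change the p-values entered into the Hommel procedure.

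The cost is SAP wording. Simulated type I error is then 0.049 and power 0.901. Timing needs care. On the protocol's proposed start (June 2014) and planned looks at 3.5, 5.0 and 6.5 years, the third interim would fall around December 2020, before the SAP version of November 2021. Actual dates are not given. The change should therefore be made by staff blinded to interim results, before unblinding, and be explained in the Final Report.
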